### **2.2.5.2 Pre-Procedure Evaluation**

Subjects who have elected to undergo implantation of the Medtronic/Talent stent gaff will undergo pre-procedure evaluation. Proper sizing and selection of the device will be based on the measurements recorded on the TAA Vessel Measurement CRF. As noted previously, information that is required for subjects in the study group include spiral CT scan results, angiogram results, dimensions of the aneurysm and aorta, the type, morphology, and clinicopathology of the aneurysm, and pre-existing risk

factors (Appendix E, Case Report Forms), as well as results of hematology, serum chemistry, and urinalysis laboratory testing, and current medications.

The following must be performed prior to implantation:

- physical examination, including femoral pulses, brachial and ankle blood pressure, and assessment of neurological functions; (Note that if any neurological deficit is observed, it must be documented and characterized on the Pre-operative Medical History CRF.)
- medical history, including concomitant medications, and demographic information.
- clinical laboratory tests:
  - hematology [CBC, platelet count, hematocrit, hemoglobin]
  - coagulation studies [prothrombin time, partial thromboplastin time, or activated partial thromboplastin time]
  - serum chemistry [sodium, potassium, chloride, bicarbonate, calcium, phosphorus, creatinine, glucose, total bilirubin, albumin, total protein, alkaline phosphatase, aspartate aminotransferase, serum glutamic pyruvic transaminase, lactic dehydrogenase, total cholesterol, triglycerides, blood urea nitrogen, uric acid].
- urinalysis

- spiral CT (recommend a minimum of 3mm slices, to adequately assess vessel dimensions)
  - angiography (with graduated marker catheter to measure/assess lengths and access vessel dimensions).

The results of all imaging studies will be verified according to mechanisms described in the Lifeline Registry for Endovascular Aneurysm Repair protocol.

### **2.2.5.3 Sizing and Selection of a Medtronic/Talent Endoluminal Stent-Graft**

Prior to the Medtronic/Talent stent-graft implant procedure, an angiogram, and a spiral CT scan, when appropriate, must be available to correctly measure and assess the aneurysm and vasculature.

#### **2.2.5.3.1 Proper-sizing of stent-graft**

For proper sizing of the Medtronic/Talent Endoluminal Stent-Graft, the information listed below must be measured and recorded on the TAA Worksheet CRF:

- diameter of the proximal aortic neck.
  - diameter of the aneurysm.
- diameter of the distal aortic neck; landing zone.
  - length of the posterior proximal aortic neck, from the proximal end of the aneurysm to the left subclavian artery, along the outer curve of the aorta.

- length of the anterior proximal neck, from the proximal end of the aneurysm to the left subclavian artery, along the inner curve of the aorta.
- aneurysm length: area of the aorta to be excluded by graft.
- length of the distal aortic neck, from the distal end of the aneurysm to the celiac trunk.
  - desired length of graft coverage.
  - access artery diameters
- sketch/tracing of aneurysm, penetrating ulcer, dissection

The condition of the arteries that will be used to access the descending aorta must also be assessed and documented to determine if access to the aneurysm can be achieved with the Medtronic/Talent Stent-Graft System. Vessel diameter, tortuosity, stenosis, plaque, etc., will affect the ease of insertion.

#### **2.2.5.3.2 Proper selection of stent-graft design**

Selection of the open web or the bare spring design at the proximal and/or distal aortic end of the stent-gaff is dependent on the length of the proximal and distal aortic aneurysm necks and proximity to the subclavian artery and celiac axis respectively. In general, the bare spring design is intended for use in cases of short proximal and/or distal aortic aneurysm necks (e.g., less than 25 mm in length). The bare spring version is designed to

allow placement of the bare spring across the left subclavian artery and the celiac axis that may be involved in the aneurysm. The open web design generally intended for use in cases of proximal and/or distal aortic aneurysm necks that are greater than or equal to 25 mm in length.

## **2.2.5.4 Treatment**

### **2.2.5.4.1 Implantation Requirements**

Equipment needed to perform a Medtronic/Talent endoluminal stent graft implantation includes:

- C-arm that can be angled freely, with the following:
  - high resolution fluoroscopy,
  - high quality angiography,
  - digital subtraction angiography.
- puncture needles, Seldinger or single needles (18G or 19G)
- Angled Glidewire (180 cm 0.035" with torque device), or equivalent
- Bentson wire (180 cm 0.035"), or equivalent
- Amplatz Super Stiff wire (260 cm 0.035") or equivalent
- Pigtail catheter (100 cm 5F multi-purpose).

- Selection of Cobra 5F, Berenstein 5F, Tegtmeyer 5F or modified DAV (Cook)
  - 5F Simmons 1, 5F Chuang 2.5
  - Snare (nitinol goose neck, 10 —15 snare diameter)
  - Non-ionic contrast (approximately 300 mg/mL)
  - Angioplasty catheters (8 mm — 20 mm, depending on cases)
  - Inflation device with pressure gauge
  - Angio introducer sheaths 5F, 6F, 7F, 8F, etc.
  - High pressure angiographic injector and extension tubing
  - High pressure flush system
  - Stopcocks (selection of 2-way and 3-way)
- Sterile placement markers to mark skin, endovascular instruments, or monitor - screens to plan precise graft placement
  - Surgical suite standby in case conventional surgical repair is necessary.

#### **2.2.5.4.2 Anticoagulation/Antiplatelet Therapy**

Patients should be heparinized during the implant procedure.

(Recommended activated clotting time is 200 - 300 seconds). An initial heparin bolus (or drip) of at least 5,000 units, followed by 1,000 units per hour bolus or drip is recommended.

#### **2.2.5.4.3 Implantation Procedure**

The following is a brief summary of the procedure. Refer to the Instructions for Use in Appendix D for further detail.

During implantation of the Medtronic/Talent Endoluminal Stent-Graft, the pre-implant angiogram and CT scan are used together with (on-the-table) intravascular ultrasound (IVUS), digital subtraction angiography (DSA), road mapping, and angiography for proper implant positioning.

The Medtronic/Talent Stent-Graft endoprostheses are inserted by delivery catheter and introducer sheath via a surgical cutdown (e.g., external iliac artery, femoral artery, common iliac artery conduit, etc.) approach. The insertion method depends on each patient's anatomy and is determined by the Clinical Investigator. The introducer sheath and delivery catheter containing the stent-graft is inserted over a guidewire and advanced into the aorta and above the aneurysm. The introducer catheter should be rotated so that the connecting bar of the compressed stent-graft is in the best position to match with bends in the target vessel.

With the delivery catheter in the correct position, the push rod is held stationary in one hand while the outer sheath is slowly withdrawn with the other hand. After

verifying that the stent-graft is in the correct position, the introducer sheath is then withdrawn further until the stent-graft is completely deployed. The balloon maybe inflated along the full length of the implanted device to model the springs against the vessel wall and to unravel possible wrinkles in the graft fabric.

After deployment of the stent-graft, angiography is performed to verify implant position and to check for the presence of endoleaks. Final arteriography is then performed to determine presence of leaks. If no leaks are detected, the introducer sheath and delivery catheter system are withdrawn from the patient. The entry site is closed by surgical means.

If endoleaks are detected during the implantation procedure, the stent-graft should be re-balloonned to ensure that the device has been properly modelled against the vessel wall. Endoleaks present after remodeling should be covered with an extension cuff; all other leaks that remain after remodeling may be treated with a cuff or may be monitored postoperatively, as determined by the Clinical Investigator. If patent collateral vessels are suspected of causing leaks, the vessels may be embolized at the Clinical Investigator's discretion. Endoleaks that are successfully treated during the endovascular operative procedure are not considered a complication or adverse event. Section 2.2.6, Adverse Events, has more information on treating endoleaks.

A Procedure form (Appendix E, Case Report Forms) will be completed after implantation has been accomplished. Fluoroscopy time and the amount of contrast material used will be recorded.

#### **2.2.5.5 Pre-discharge**

Prior to hospital discharge, a pre-discharge examination will be completed for all study group patients. This will include a physical examination and laboratory testing (including hematology, serum chemistries, and urinalysis). The spiral CT may be done at any appropriate interval within four weeks after the date of implantation. Any new (or worsened) neurological deficits observed post-procedure require a neurological consult.

#### **2.2.5.6 Post-Discharge Follow-up**

After hospital discharge, patients will be seen 1, 6, and 12 months (30 days) and annually for life after the implant procedure with annual reports to be submitted to the FDA based on a 5-year data. Patients may also be seen for additional follow-up visits, if clinically appropriate. Post-

Operative Assessment form (Appendix E) will be completed for each visit.

At each post-discharge examination, patient status, vasculature and aneurysm status, and device efficacy will be assessed. Any new (or worsened) neurological deficits observed post-procedure require a neurological consult. If additional follow-up visits occur, information obtained at that visit will be recorded on the Post-Operative Assessment form.

#### **2.2.5.7 Final Assessment**

Subjects who have completed 12 months of follow-up will continue annual follow-up examinations for life with annual reports submitted to the Food and Drug Administration for 5 years. These follow-up visits will include a physical examination, a CT, and a plain film x-ray as defined in the Chart of Study Procedures (Appendix F). Subjects who received a Medtronic/Talent stent-graft implant and who choose to discontinue participation in the study prior to study completion will be contacted to perform a final assessment prior to study closure. The final assessment will be recorded on Post-Operative Assessment and Termination CRFs.

A Termination Case Report Form will be completed for every subject regardless of the reason for study termination. A chart may be found in Appendix F indicating the times at which procedures and tests will be performed.

#### **2.2.6 Adverse Events**

Any adverse experiences reported by a subject in the study or noted by the Clinical Investigator/Sponsor, will be reported on the Post-Operative Assessment CRF (Appendix E). Each experience must be categorized by the Clinical Investigator/Sponsor by its degree of severity (mild - the event did not require treatment, moderate - the event was treated locally or by minimally invasive treatment, or severe - the event was fatal or resulted in permanent injury or disability), its relationship to study device and implantation procedure (not related,

associated with, caused by), and whether or not the adverse experience was unanticipated. An unanticipated adverse effect as defined by the FDA is any serious adverse effect on the health and safety or any life-threatening problem or death caused by, or associated with, a device, if that effect, problem or death was not previously identified in nature, severity or degree of incidence in the investigational plan or application (including a supplementary plan or application), or any other unanticipated serious problem associated with a device that relates to the rights, safety or welfare of subjects (Section 812.3). Refer to Appendix D, Instructions for Use, and the Study Subject Informed Consent (Appendix H) for a listing of known events.

Adverse events are to be scored as follows:

=None; the event was not observed

=Mild; the event was observed, but no treatment was required or the event resolved without treatment

=Moderate; the event was treated locally or by minimally invasive means

=Severe/Serious as defined below

- life-threatening (or fatal).
- results in permanent impairment of a body function or permanent damage to a body structure; or
- necessitates medical or surgical intervention to preclude permanent impairment of body function or permanent damage to a body structure.

The Clinical Investigator/Sponsor will report all unanticipated, device deterioration events to the FDA.

Historical data have demonstrated that several types of complications are known to occur with this procedure. These complications are described in the following sections

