#### **2.2.4 Study Design**

This study is a prospective evaluation of patients receiving the investigational device to determine the proportion in whom successful implantation is achieved, as indicated by aneurysm exclusion and graft patency at implant, time of discharge, and 1-, 6-, and 12-months following implantation, and to determine the proportion of patients who experience adverse events during and after the implantation procedure, including comorbidities and overall mortality rates. The percentage of patients in whom technical and clinical success is achieved, and the percentage who experience serious adverse effects will be determined. Additional endpoints that will be evaluated are length of stay in intensive care following the procedure, total length of hospital stay and recovery time.

Patient data and follow-up information and images will be stored with the Lifeline Registry for Aneurysm Repair with periodic reports to the FDA up to the 5-year follow-up supplemented with reports from the Registry database.

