#### **2.2.6.1 Endoleaks**

Immediately after placement of the Medtronic/Talent Endoluminal Stent-Graft, or upon later evaluation, endoleaks may be detected. Endoleaks are considered any extravasation of contrast outside of the flow channel established by the stent-graft. For purposes of this study, endoleaks that are detected and corrected during the implantation procedure are not considered a complication of the Talent device or procedure. However, uncorrected endoleaks that develop during implantation or endoleaks that develop after implantation are considered complications and must be reported on the Procedure or Post-Operative Assessment CRF. The type and possible cause of the endoleak should be noted on the CRF.

Treatment of endoleaks is at the discretion of the Clinical Investigator/Sponsor. In general, it is recommended that endoleaks be corrected during the initial procedure unless the Clinical Investigator believes that there is a likelihood that the endoleak

may spontaneously seal after a few days. The decision to intervene at later intervals will be based on the severity of the endoleak, the possible cause of the endoleak, the status of the aneurysm, and the subject's general health. Known or suspected endoleaks must be monitored carefully postoperatively with appropriate diagnostic imaging.

Attempts to correct postoperative endoleaks may be done by any of the following procedures:

- using an endovascular balloon to remodel the stent-graft near the endoleak.
- implanting an extension cuff over the endoleak; or
- surgical intervention.

Any procedure performed to correct postoperative endoleaks will be recorded on the Post-Operative Assessment CRF.

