### **2.2.6.4 Other Adverse Events**

The health risks associated with use of the Medtronic/Talent Endovascular System may be less than for conventional surgical treatment. However as with any medical procedure, there are some risks. There is the potential for discomfort or complications resulting from the procedure and the implanted Stent-Graft. It is hypothesized that the rate of serious adverse events in stent-graft patients will be less as compared to an expected serious adverse event rate for surgical patients.

Following is a non-exhaustive list of potential serious complications that may occur during or following implantation of a Medtronic/Talent Endoluminal Stent-Graft:

- distal or proximal embolization that may lead to stroke, amputation, kidney failure, multiple organ failure, or death.
- renal insufficiency or failure, that may necessitate dialysis.
  - immediate leaking into the aneurysm, possibly leading to rupture of the aneurysm and death;
- later leaking into the aneurysm, possibly leading to rupture of the aneurysm and death.
- vessel rupture, possibly leading to shock, conversion to surgery, or death.
- migration of the device, possibly leading to rupture of the aneurysm, open surgery, or death.
- blood loss, possibly leading to shock or death.
  - gaff twisting or kinking, possibly leading to shock or death.
- infection, possibly leading to septicemia or death.
- occlusion of blood flow to the spinal cord, possibly leading to temporary or permanent paraparesis or paraplegia;
- conversion to open surgery with all the risks associated with an open surgical repair;

- myocardial infarction, arrhythmia and/or congestive heart failure possibly leading to shock or death.
- respiratory failure possibly leading to death.

Similarly, there are a number of minor risks and discomforts that could result from the implant procedure or adjunctive tests/analyses. The following is a summary of those potential discomforts.

- Heart and lung testing may involve some discomfort.
- Blood collection may cause bruising and/or discomfort.
- The CT and angiography procedures may cause discomfort during scanning but should not cause pain.
- The radiopaque dyes used during CT and angiography procedures can cause nausea, vomiting, or other reactions.
- Some pain and bruising at the site may result in the groin where the device is insertero

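### A temporary paraparesis or paraplegia that resolves untreated scores Mild under Protocol 2.2.6, although 2.2.6.4 names it under potential serious complications; a serious-event percentage taken from that score would miss it.

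*Protocol*

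**What the plan says.** Section 2.2.6 gives severity twice. The opening paragraph has a three-level scale whose top level reads "severe - the event was fatal or resulted in permanent injury or disability". The scoring list further down has None, Mild, Moderate and Severe/Serious. Mild is "the event was observed, but no treatment was required or the event resolved without treatment". Moderate means treated locally or by minimally invasive means. Severe/Serious has three alternative criteria: the event is life-threatening or fatal; it "results in permanent impairment of a body function or permanent damage to a body structure"; or it "necessitates medical or surgical intervention to preclude permanent impairment of body function or permanent damage to a body structure".

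Section 2.2.6.4 then introduces its risk list: "Following is a non-exhaustive list of potential serious complications that may occur during or following implantation". One entry is "occlusion of blood flow to the spinal cord, possibly leading to temporary or permanent paraparesis or paraplegia".

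The result at stake is in 2.2.4, where "the percentage who experience serious adverse effects will be determined". Section 2.2.6.4 also hypothesizes a serious adverse event rate below that expected for surgery, without giving a figure. No text says whether the score, the earlier scale or the list in 2.2.6.4 decides what is serious for that percentage.

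**The concern.** The lower grades depend on what was done about an event, not on what happened to the patient. A spinal cord deficit that clears untreated therefore lands in the lowest grade above None, although the protocol itself mentions temporary deficits when it describes serious complications. This is not an overlap between two grades that a rule of taking the higher grade could settle, because no higher grade applies.

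Safety is the primary objective (2.1.2), and the percentage with serious events is a main safety result. The grade is assigned when the event goes on the case report form. If treatment and resolution are folded into the grade, an analysis plan written later may not be able to recover them.

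**Working it through.** **Step 1: apply the scoring list.** Take a new paraparesis or paraplegia after implantation that is not life-threatening, recovers, and neither needed nor received treatment.

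| Rule in 2.2.6 | Met? |
|---|---|
| Severe/Serious: life-threatening or fatal | No, by assumption |
| Severe/Serious: permanent impairment or damage | No, it was temporary |
| Severe/Serious: intervention needed to prevent permanence | No, none was needed |
| Moderate: treated locally or minimally invasively | No, untreated |
| Mild: no treatment required, or resolved untreated | Yes |

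The score is Mild. The opening scale of 2.2.6 gives the same answer, since the event is neither fatal nor permanent.

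**Step 2: vary the case.** A permanent deficit is Severe/Serious on both scales. A temporary deficit that needed intervention to prevent permanent impairment is Severe/Serious on the scoring list, but not severe on the opening scale. So the two scales in 2.2.6 also disagree with each other on treated, recovered deficits.

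**Step 3: size.** The protocol states no serious-event rate, so there is no figure to reproduce. Inputs:
- n = 50 planned subjects (2.1.3)
- 4 cases of paraplegia in 108 patients in the cited endoluminal stent-graft series (1.1)
- f, the share of such cases that are temporary, untreated and not life-threatening. The documents do not give it, so it is run from 0 to 1.

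One patient: 1/50 = 2 percentage points, if that patient has no other serious event.

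Cited frequency: 4/108 = 3.7%. Expected cases in 50: 50 × 4/108 = 1.85.

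With p = f × 4/108, the expected number of affected patients is 50p, the average understatement is 100p points (again assuming no other serious event in those patients), and the chance of at least one affected patient is 1 − (1 − p)^50:

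| f (assumed) | Expected patients in 50 | Average understatement (points) | Chance of at least one |
|---|---|---|---|
| 0 | 0 | 0 | 0 |
| 0.25 | 0.46 | 0.9 | 0.37 |
| 0.5 | 0.93 | 1.9 | 0.61 |
| 0.75 | 1.39 | 2.8 | 0.76 |
| 1 | 1.85 | 3.7 | 0.85 |

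The table covers paraplegia only. The series as cited gives no count of paraparesis and no split into temporary and permanent cases.

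**The case against.** **The list in 2.2.6.4 is a risk warning, not a classification.** The listed item is spinal cord occlusion, with a temporary deficit as one possible result, and a potentially serious complication can have a mild instance. This is fair, and it means that 2.2.6.4 cannot be read as a rival scoring rule. It does not remove the mismatch: the protocol names the temporary form under a serious heading, and its scoring list has no place for it above Mild.

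**The link from score to percentage is inferred.** This also stands. Section 2.2.4 does not say where its serious events come from, and an analysis plan could settle it. But the scoring list is the only operational definition of Severe/Serious in the protocol. If it is not the source, the protocol leaves the meaning of serious for that percentage open.

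**The events remain visible.** All adverse experiences are reported, and any new or worsened neurological deficit requires a neurological consult (2.2.5.5, 2.2.5.6). That secures evaluation but does not change the score.

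**Endoleaks.** A reader might infer that observed endoleaks leave the serious percentage in the same way, since "Treatment of endoleaks is at the discretion of the Clinical Investigator/Sponsor". The text gives little support. Leaks left uncorrected at implantation or arising later are reportable complications whether or not they are treated (2.2.6.1). A leak treated by balloon or cuff can itself score Moderate, so choosing observation would often move Moderate to Mild and leave the serious percentage unchanged. A persisting leak that needs treatment but is left alone does not fit Mild at all.

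**Conclusion.** The point holds in limited form. A temporary, untreated, non-life-threatening paraparesis or paraplegia scores Mild under 2.2.6, in tension with 2.2.6.4, and is not counted if the serious-event percentage is taken from the score. The size is 2 points per affected patient with n = 50. On average it is 0 to 3.7 points at the cited paraplegia frequency, and the upper end requires every such case to be temporary and untreated.

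Two stronger readings are not supported:
- **That neurological events in general drop out.** Permanent deficits, life-threatening ones and those needing intervention to prevent permanent impairment stay Severe/Serious on the scoring list.
- **That the comparison with surgery is biased in favour of the device.** The omission lowers the device percentage, but the protocol gives neither a surgical rate nor a definition of what that rate counts. The net effect on the comparison is unknown.

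**What to change.** Reconcile 2.2.6 and 2.2.6.4 by adding one sentence to the scoring list:

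> For the serious adverse event percentage, stroke and any new paraparesis or paraplegia, temporary or permanent, count as Severe/Serious whether or not the event was treated or has resolved.

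Record treatment and resolution in their own fields on the case report form. State that this one definition feeds the percentage in 2.2.4 and the rate in 2.2.6.4, and let it replace the differing severe wording in the opening paragraph of 2.2.6.

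Do not extend the rule to everything named in 2.2.6.4. That would make any blood loss or arrhythmia serious. It would also clash with 2.2.5.4.3 and 2.2.6.1, under which leaks corrected during the procedure are not complications.

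The cost is a few lines of text, the added form entries, and a reported serious-event percentage that may be slightly higher.

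### Section 2.2.6 defines the top severity grade in two different ways, and in its scoring list Moderate overlaps Severe/Serious with no rule on which prevails

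*Protocol*

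**What the plan says.** Section 2.2.6 of the protocol contains two grading instructions, both worded as requirements.

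- **Opening paragraph.** "Each experience must be categorized by the Clinical Investigator/Sponsor by its degree of severity". In the parenthesis that follows, the middle grade is "moderate - the event was treated locally or by minimally invasive treatment" and the top grade is "severe - the event was fatal or resulted in permanent injury or disability".
- **Scoring list.** "Adverse events are to be scored as follows". The grades are None, Mild, Moderate and Severe/Serious. The third is "Moderate; the event was treated locally or by minimally invasive means". The fourth applies if any of three criteria is met: the event is life-threatening or fatal; it causes permanent impairment or damage; or it "necessitates medical or surgical intervention to preclude permanent impairment of body function or permanent damage to a body structure".

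Three other sections bear on how the grades are used:

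- Section 2.1.2 makes safety the primary objective.
- Section 2.2.4 commits the study to determining the percentage of patients with serious adverse effects.
- Section 2.2.6.4 hypothesises a lower serious event rate than expected with surgery, without giving a figure.

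On endoleaks, section 2.2.6.1 says that "endoleaks that develop after implantation are considered complications and must be reported on the Procedure or Post-Operative Assessment CRF". It names balloon remodelling, an extension cuff and surgery as ways to correct them, and adds that "Treatment of endoleaks is at the discretion of the Clinical Investigator/Sponsor".

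**The concern.** The two top grades do not cover the same events. The opening paragraph leaves out non-fatal life-threatening events and events where intervention averted permanent harm; the list includes both. An investigator cannot follow both instructions for such an event.

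The list also has a difficulty of its own. Moderate is defined by the route of treatment and the third Severe/Serious criterion by its purpose, so one event can satisfy both. The section does not say that the grades exclude each other or that the higher one prevails.

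Minimally invasive correction is characteristic of an endovascular device, so the ambiguity falls on a kind of event the protocol expects. The person who scores the event is the Clinical Investigator/Sponsor, and choosing Moderate lowers the serious event percentage.

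**Working it through.** The protocol states no figure to reproduce. The check is to grade the same events under both instructions in section 2.2.6.

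| Event | Opening paragraph | Scoring list |
|---|---|---|
| Fatal | severe | Severe/Serious |
| Permanent injury | severe | Severe/Serious |
| Treated locally, no threat of lasting harm | moderate | Moderate |
| Non-fatal but life-threatening, treated by minimally invasive means, full recovery | moderate | Moderate **and** Severe/Serious (first criterion) |
| Minimally invasive intervention needed to prevent permanent damage, full recovery | moderate | Moderate **and** Severe/Serious (third criterion) |
| Open surgery needed to prevent permanent damage, full recovery | no grade fits | Severe/Serious (third criterion) |

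The scales agree on the first three types. On the other three they differ, or the list gives two answers.

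The protocol foresees events of these kinds. Balloon or cuff correction of a postoperative endoleak (2.2.6.1) falls in the fifth row when it was needed to prevent permanent harm and left none. Not every treated endoleak qualifies, because treatment is discretionary. Open conversion (2.2.6.2) falls in the last row when it meets the third criterion and the patient recovers fully.

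Section 2.2.6.4 lists later leaking into the aneurysm among potential serious complications. That favours the serious reading for endoleaks, but the list assigns no grade.

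**Effect on the reported percentage.** The input is the 50 subjects of section 2.1.3.

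- One patient whose only qualifying event is scored Moderate instead of Severe/Serious: 1/50 = 0.020, or 2.0 percentage points.
- The protocol gives no basis for the number of such patients. If it were 1 to 5 (an assumption), the shift would be 1/50 to 5/50, or 2 to 10 points.
- Section 2.2.3 removes patients found ineligible after implant from the final analysis, so the denominator may be below 50 and the step slightly larger. With 45 analysed (again an assumption) it would be 1/45 = 2.2 points.

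The prior series in section 1.1 do not narrow this range. One reports no endoleaks in 12 stent-graft patients. The other reports complete thrombosis and technical success in 103 of 108, without a count of corrected endoleaks.

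**The case against.** The best reply is that the scoring list is ordinal. Only its top grade has explicit criteria, joined by 'or', so an event that meets any of them is Severe/Serious, and Moderate is what remains among treated events. Only the list uses the word serious as a grade, so the section 2.2.4 percentage would naturally rest on it. The opening paragraph would then affect a severity descriptor and not the reported figure.

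That reading is reasonable and many investigators would adopt it. The protocol does not state it, however, and the opening paragraph grades the overlapping events with minimally invasive treatment as moderate. Either score therefore has support in the text.

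Several further points stand in part:

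- The case report forms are not available here and might carry a precedence rule. Section 2.2.6 refers to none, and a rule on a form would leave the two definitions in conflict.
- Recorded severity *may* be inconsistent; it need not be, if everyone follows the list.
- The 2.0 points are what any one patient contributes in a study of 50, so they give the size of a step and not an expected shift.
- A precedence rule would not remove judgement. Someone must still decide whether an intervention was needed to prevent permanent harm. It would remove the freedom to score an event Moderate after that judgement has been made.

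**Conclusion.** The concern holds. Section 2.2.6 gives two incompatible definitions of its top grade, and within the scoring list Moderate overlaps Severe/Serious without a stated precedence. The conflict between the definitions is plain on the text. The overlap rests on the absence of any precedence rule in the protocol, with the case report forms unseen.

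The consequence is limited. The events are not lost, because procedures for endoleaks and conversions to surgery are recorded on case report forms whatever their grade. No numeric comparator or threshold is stated, so no stated decision changes. What is exposed is the consistency of recorded severity and the percentage with serious adverse effects.

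This should be corrected in the protocol and not left to an analysis plan. Grades are assigned when events are reported, and the reason for an intervention cannot be reliably recovered afterwards.

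**What to change.** Make three changes in section 2.2.6:

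1. Align the severity definitions in the opening paragraph with the scoring list, or delete them.
2. State that an event meeting any of the three Severe/Serious criteria is scored Severe/Serious and counts in the section 2.2.4 percentage, whatever the route of treatment.
3. Limit Moderate to events that meet none of the three criteria.

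The case report forms should carry the same wording. The cost is a few words of text. The reported serious event percentage may be somewhat higher than if overlapping events were scored Moderate.
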